4.4.2.2.8 Survival

This endpoint will be summarized for low dose and the high dose groups separately for all participants in the FAS. Kaplan-Meier plots of time from the dosing date to event will be provided. In addition, the estimated survival rate at the following time-points will be presented by dose level group:

- 3 months
- 6 months
- 1 year
- 2 years
- 5 years
- 10 years

For this analysis, the date of a participant's death is considered the time of an event. Survival status should be assessed at each visit until the participant withdraws consent or completes the study. If the participant misses a visit or withdraws for a reason other than withdrawal of consent or death, the site should contact the parent(s)/LAR(s) to ascertain if the participant is

alive. For participants who withdraw from the study, the participant should be contacted every 6 months for 5 years after administration and every year for an additional 5 years (after the 5-year follow-up through 10-years follow-up) to assess for survival. If not alive, the cause and date of death should be requested and recorded.

Participants will be censored at the last known date/time of contact.

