7.4.2.2 Other Secondary Efficacy Endpoints

The analysis of other secondary efficacy endpoints will be conducted using the FAS.

Time to reduction in required daily ventilator support to \leq 16 hours by Week 24, time to reduction of at least 6 hours in daily ventilator support by Week 24, and time to death will be summarized for low dose and high dose. Kaplan-Meier plots along with median (95% CI) time from the study start date to event will be provided.

The CHOP INTEND, MIP, ACEND, and PedsQL, as well as their changes from baseline, will be summarized descriptively over time, and the changes from baseline will be analyzed using the MMRM in a similar method to that used for the primary analysis of the primary efficacy endpoint.

The number and percentage of subjects attaining age-appropriate clinically relevant gross motor function milestones through Week 24, and subjects achieving full ventilator independence at Week 24, will be summarized for low dose and high dose.

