3 ANALYSIS SETS

In accordance with International Conference on Harmonization (ICH) recommendations in guidelines E3 and E9, the following analysis sets will be used for the analyses.

The determination of whether participants are included or excluded from the safety and efficacy analysis sets will be made prior to database lock.

The following analysis sets for participants treated with AT132 will be used:

- Full Analysis Set (FAS) is defined as all randomized and/or enrolled participants who received AT132 and had at least 1 postdose efficacy assessment. The participants will be analyzed based on the treatment actually received. The FAS will be used for summary of demographics and baseline characteristics, and analyses of all efficacy endpoints.
- Safety Analysis Set (SAF) is defined as all randomized and/or enrolled participants who received AT132. The participants will also be analyzed based on the actual treatment received as well as an “All dosed” group of all participants treated with AT132. The SAF will be used for summaries of demographics, baseline characteristics, participant disposition, and the analysis of the safety endpoints.

In each analysis set, 3 treatment groups are defined by: (i) Low Dose (AT132 1.3×10^{14} vg/kg), (ii) High Dose (AT132 3.5×10^{14} vg/kg), and (iii) AT132 Dosed Total (not applicable to efficacy endpoints).

Listings will include all randomized participants unless otherwise stated.

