4.4.2.2 Main Analytical Approach

The secondary efficacy analyses will be conducted for the FAS.

4.4.2.2.1 Time to reduction in required ventilator support to ≤ 16 hours a day (only in participants who require invasive ventilation) at Week 24

This endpoint will be summarized for low dose and the high dose groups separately in the participants who require invasive ventilation. Kaplan-Meier plots along with median (95% CI) time from the study start date to event will be provided.

The number of hours of ventilator support at each collected time point for this analysis will be taken directly from the daily diary (Protocol V5.0 and later) or by assessment of time off ventilator questionnaire (prior to Protocol V5.0). The first instance of time reduction reported as ≤ 16 hours per day will be considered an event. Participants will be censored at either Week 24 or withdrawal from study, whichever occurs first.

4.4.2.2.2 Change from baseline in Children's Hospital of Philadelphia Infant Test of Neuromuscular Disorders (CHOP INTEND) at Week 24

The change from baseline will be analyzed using the MMRM in a similar method to that used for the primary analysis of the primary efficacy endpoint, described in [Section 4.3.2](#).

Estimated change from baseline in CHOP INTEND score at Week 24 will be summarized by dose level.

In addition, the CHOP INTEND score and corresponding change from baseline at each visit will be summarized descriptively by dose level group.

The CHOP INTEND is an assessment scale that was originally designed to quantify motor abilities in infants aged 1.4 to 37.9 months, with spinal muscular atrophy type I (SMA-I) ([Glanzman, 2010](#)) and has been validated for XLMTM ([Duong, 2021](#)). The scale contains 16 questions, each of which is scored on a scale of 0 to 4, with 0 being no response/ability to perform the movement and 4 highest ability to perform the task, per CHOP INTEND item instructions.

The score used for analysis is the total sum of all 16 questions, which will range from 0 to 64. Higher score indicates better neuromuscular function. If an item is missing or scored as "Could Not Test (CNT)" then 0 will be imputed for the item score.

If a participant has 2 assessments with a total score of ≥ 56 , the CHOP INTEND will not be required for future visits.

Subject line plots of the CHOP INTEND over time will be created.

4.4.2.2.3 Change from baseline in maximal inspiratory pressure (MIP) at Week 24

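### Survival is estimated from the dosing date in a set that requires a later efficacy assessment, so a dosed child who died before one would be left out of the curve

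*SAP*

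**What the plan says.** SAP 4.4.2.2.8 (Survival) sets the population: "This endpoint will be summarized for low dose and the high dose groups separately for all participants in the FAS". It also sets the time origin: "Kaplan-Meier plots of time from the dosing date to event will be provided". Survival rates are to be shown by dose group at 3 months, 6 months, and 1, 2, 5 and 10 years, with censoring at the last known contact.

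SAP section 3 defines the two analysis sets:

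- "Full Analysis Set (FAS) is defined as all randomized and/or enrolled participants who received AT132 and had at least 1 postdose efficacy assessment".
- "Safety Analysis Set (SAF) is defined as all randomized and/or enrolled participants who received AT132".

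The choice of the FAS appears in more than one place. SAP section 3 assigns it to every efficacy endpoint. SAP 4.4.2.2 states: "The secondary efficacy analyses will be conducted for the FAS". Protocol 7.4.2.2 (Other Secondary Efficacy Endpoints), which covers time to death, states: "The analysis of other secondary efficacy endpoints will be conducted using the FAS".

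Neither document exempts survival from the FAS condition or plans a supportive survival curve in the SAF. Neither says that a death or a survival check counts as the qualifying efficacy assessment.

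**The concern.** A survival curve that starts at dosing should have everyone who was dosed at risk at time zero. Here a child enters the set only if an efficacy assessment is recorded after dosing. A child who dies in that gap drops out of both the event count and the number at risk. Selection then depends on the outcome being estimated, and for a death the effect is to raise estimated survival.

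The groups are small, and Protocol 1.5 describes four fatal outcomes after AT132, one at the low dose and three at the high dose. In groups of this size one child moves the estimate visibly. An early death that is left out also affects every later time point on the curve, not only the 3-month rate. Ascertaining death needs no efficacy form, so the FAS condition serves no purpose for this endpoint.

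**Working it through.** The plan states no expected survival rate, event count or sample size for this endpoint, so there is no planned figure to reproduce. The check sets the definitions side by side and then illustrates the size.

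**Step 1: the definitions**

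| | FAS | SAF |
|---|---|---|
| Received AT132 | required | required |
| Efficacy assessment after dosing | at least one | not required |
| Used for survival | yes | no |
| Used for the tables of deaths and fatal adverse events (SAP 4.6, 4.6.1) | no | yes |

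The FAS and SAF can differ only by dosed children with no efficacy assessment after dosing. Such a child either died or left the study alive before the first assessment.

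**Step 2: how long the gap is**

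- The schedule in Protocol 5.4 places ACEND, PedsQL, the clinical global impression scales and the swallowing, speech and communication questionnaires at Week 1 (Day 7 ± 1).
- Under protocol v5 and later, the caregiver's ventilator diary starts after consent and is completed daily (Protocol 5.1.1.11.2.1). A qualifying record could therefore exist within days of dosing, without a visit.
- Children dosed under v4 or earlier have no diary at baseline (SAP 4.3.1). SAP 4.4.2.2.6 describes Bayley and motor milestone collection under v1 to v4 as intermittent.
- In all four fatal cases bilirubin began to rise 1 to 4 weeks after dosing (Protocol 1.5), so death came later than that. No dates of death are given.

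The gap is therefore short, and the four described deaths probably fall after it.

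**Step 3: inputs for the illustration**

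- Low dose: 6 dosed at the 08 July 2020 cutoff (Protocol 1.4.2). Three controls were then undosed (SAP 1.2) and two were never dosed (SAP 1.3), which gives 6 + (3 − 2) = 7. This assumes that no replacement was enrolled.
- High dose: 17 at the same cutoff (Protocol 1.4.2). This assumes that none was dosed at that level later.
- Deaths D: 1 low dose, 3 high dose (Protocol 1.5). Deaths from other causes are not described.

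**Step 4: size**

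With N dosed, D deaths and k deaths before the first efficacy assessment, crude survival is (N − D)/N in the SAF and (N − D)/(N − k) in the FAS.

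| Group | SAF | FAS, k = 0 | FAS, k = 1 | FAS, k = 2 | FAS, k = 3 |
|---|---|---|---|---|---|
| Low dose | 6/7 = 85.7% | 6/7 = 85.7% | 6/6 = 100% | n/a | n/a |
| High dose | 14/17 = 82.4% | 14/17 = 82.4% | 14/16 = 87.5% | 14/15 = 93.3% | 14/14 = 100% |

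One exclusion raises the estimate by 14.3 points at the low dose (100 − 85.7) or 5.1 points at the high dose (87.5 − 82.4). With k = 0 the two sets agree on these deaths.

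If the excluded death comes first, with all N children at risk, the full Kaplan-Meier curve equals (N − 1)/N times the curve of the rest. Leaving that child out therefore multiplies every later rate by N/(N − 1): 7/6 = 1.167 at the low dose and 17/16 = 1.063 at the high dose.

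**Step 5: a child who left alive**

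If a child withdrew before any assessment but was traced alive, leaving that child out lowers crude survival: low dose 6/7 (85.7%) to 5/6 (83.3%), high dose 14/17 (82.4%) to 13/16 (81.3%). If that child was censored almost at once, the curve hardly changes.

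**The case against.** The strongest answer is that the condition will probably exclude nobody. Week 1 carries several efficacy instruments, later subjects have a daily diary already running at dosing, and the four described deaths followed liver abnormalities that began weeks after dosing. This stands, and it keeps the point small. It does not close it: the documents give no dates of death and no FAS or SAF counts, and early data collection was thinner under v1 to v4.

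Second, no death is hidden. Deaths and fatal adverse events are tabulated in the SAF by dose and period (SAP 4.6, 4.6.1), the disposition table reports the size of both sets (SAP 4.2.1), and all analyses are descriptive (SAP section 2). This also stands. A reader might infer that early deaths would vanish from the report, and the documents do not support that. However, the SAF tables do not correct the survival curve or its 3-month to 10-year rates, and the report could then carry two different death counts.

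Third, survival is itself a listed efficacy endpoint and status is checked at visits: "Survival status should be assessed at each visit until the participant withdraws consent or completes the study". It could be argued that a survival check qualifies a child for the FAS. The SAP does not say so, and that reading would leave the FAS condition with almost no content.

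A reader might also infer that the rule can only raise survival. That is too strong. A child who withdrew alive before any assessment would be dropped as well, and withdrawn children may still be followed for survival (Protocol 5.1.1.25; SAP 4.4.2.2.8). The upward bias applies to an excluded death, not to every possible exclusion.

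**Conclusion.** The point holds as a defect in the rule, of low priority. Survival measured from dosing is conditioned on a later event, and a death before that event would bias the estimate upward. If it happened once, the shift would be about 14 points at the low dose or 5 points at the high dose, on inferred counts of 7 and 17. Those counts assume that no replacement was enrolled and that no high-dose dosing took place after July 2020.

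A reader might conclude that a death has in fact been excluded, or that reported survival will be overstated. The documents do not show this, and what they say about timing makes it unlikely. They do not rule it out either. The case for changing the set is that the SAF matches the time origin, needs no judgement about which records qualify, and costs almost nothing.

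**What to change.** Analyse survival in the SAF, by the same dose groups:

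- In SAP 4.4.2.2.8, name the SAF instead of the FAS.
- In SAP section 3 and SAP 4.4.2.2, add a matching exception for survival. Both now assign the FAS without exception, so changing 4.4.2.2.8 alone would leave the SAP contradicting itself.
- In the study report, note the departure from Protocol 7.4.2.2. Protocol section 7 already provides that the final SAP prevails and that reasons for differences are reported.

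A weaker alternative is to state that a death or a recorded survival status satisfies the FAS condition. That would change the FAS for every efficacy endpoint and so needs more thought.

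The preferred change costs a few words in three places and a sentence in the report. It needs no new data, and results are identical if the FAS and SAF contain the same children.

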4.5 Exploratory Endpoints Analysis

The analysis of exploratory efficacy endpoints will be conducted using the FAS.

4.5.1.1 Definition of Endpoints

- Time to unassisted sitting for 30 seconds or more at Week 24
- Change from baseline in the Motor Function Measure-32 (MFM-32) at Week 24
- Change from baseline in total raw score in the gross motor domain of the Bayley Scales of Infant and Toddler Development III (Bayley-III) at Week 24
- Change from baseline in total raw score in the fine motor domain of the Bayley-III at Week 24
- Change from baseline in the proportion of participants being able to feed without a gastrostomy or G-tube at Week 24
- Change from baseline in the Communicative Development Inventories scores at Week 24
- Change from baseline in the Parental Global Impression of Secretion Severity (PGIS-S) score at Week 24
- Change in the Parental Global Impression of Secretion Improvement (PGIS-I) score at Week 24
- Change from baseline in Clinical Global Impression of Severity (CGI-S) at Week 24
- Change in the Clinical Global Impression of Improvement (CGI-I) score at Week 24

4.5.1.2 Main Analytical Approach

4.5.1.2.1 Time to unassisted sitting for 30 seconds or more at Week 24

This endpoint will be summarized for low dose and the high dose groups separately for all participants in the FAS. Kaplan-Meier plots along with median (95% CI) time from the study start date to event will be provided.

The event of successful unassisted sitting for 30 seconds is defined as described in [Section 4.4.1.1](#). Participants who meet the described criteria will be considered to have an event. All other participants will be censored

4.5.1.2.2 Change from baseline in the Motor Function Measure-32 (MFM-32) at Week 24

MFM-20 and MFM-32 total and dimension scores will be summarized descriptively by visit and dose level group. For the MFM-20 by-visit summary, if participants were administered the MFM-32, then the MFM-20 questions/derivations will be used from those assessments to derive the MFM-20 result for summary purposes.

Regardless of whether the participants were administered MFM-32 or MFM-20, the observed total and dimension scores and corresponding change from baseline at each visit will be listed. The listing will include a column indicating which version of the questionnaire was administered at the visit.

4.5.1.2.2.1 MFM-32 Scoring

The MFM-32 contains 32 items to assess motor function, each measured on a scale of 0 to 3, for a total score of 96. The measures capture 3 dimensions of motor function:

- Standing and transfers (D1: 13 Items 6, 8, 11, 12, 24, 25, 26, 27, 28, 29, 30, 31 and 32)
- Axial and proximal motor function (D2: 12 Items 1, 2, 3, 5, 7, 9, 10, 13, 14, 15, 16 and 23)
- Distal motor function (D3: 7 Items 4, 17, 18, 19, 20, 21, and 22)

The score for each dimension corresponds to the sum of the scores obtained by the person for the items of this dimension divided by the maximum score for this dimension and multiplied by 100. For the unilateral items, the best score of the two sides at each visit will be used.

For the MFM-32, the total score is the sum of the 32 items scores divided by 96, as shown in the table below:

Table 2 MFM-32 Scoring

Measurement	Calculation
D1: Standing and Transfers	$D1\% = \frac{\text{Sum of D1 score}}{13 \times 3 = 39} * 100$
D2: Axial and Proximal	$D2\% = \frac{\text{Sum of D2 score}}{12 \times 3 = 36} * 100$
D3: Distal Motor Function	$D3\% = \frac{\text{Sum of D3 score}}{7 \times 3 = 21} * 100$
Total	$\text{Total}\% = \frac{\text{Sum of total score}}{32 \times 3 = 96} * 100$

When all items are missing, the total score will be missing. When there are some missing item scores (but other items are available), the score for the missing item(s) will be imputed as 0.

4.5.1.2.2.2 MFM-20 Scoring

The MFM-20 was developed after the original MFM-32, and is a subset of the MFM-32 questionnaire. Items from the MFM-32 that are not considered validated for the <6 years old population are skipped for the administration of the MFM-20, though the numbering of the items remains the same.

The MFM-20 contains 20 items assessing motor function, each measured on a scale of 0 to 3, for a total score of 60. The measures capture 3 dimensions of motor function:

- Standing and transfers (D1: 8 Items 6, 11, 12, 24, 25, 27, 30, 32)

- Axial and proximal motor function (D2: 8 Items 1, 3, 5, 7, 9, 10, 14, 23)
- Distal motor function (D3: 4 Items 4, 18, 21, 22)

The score for each dimension corresponds to the sum of the scores obtained by the person for the items of this dimension divided by the maximum score for this dimension and multiplied by 100. For the unilateral items, the best score of the two sides at each visit will be used. For the MFM-20, the total score is the sum of the 20 items scores divided by 60, as shown in the table below:

Table 3 MFM-20 Scoring

Measurement	Calculation
D1: Standing and Transfers	$D1\% = \frac{\text{Sum of D1 score}}{8 \times 3 = 24} * 100$
D2: Axial and Proximal	$D2\% = \frac{\text{Sum of D2 score}}{8 \times 3 = 24} * 100$
D3: Distal Motor Function	$D3\% = \frac{\text{Sum of D3 score}}{4 \times 3 = 12} * 100$
Total	$\text{Total}\% = \frac{\text{Sum of total score}}{20 \times 3 = 60} * 100$

The same missing data conventions described in [Section 4.5.1.2.2.1](#) will be used for the MFM-20 scoring.

4.5.1.2.3 Change from baseline in total raw score in the gross motor domain of the Bayley Scales of Infant and Toddler Development III (Bayley-III) at Week 24

The raw Bayley-III gross motor domain scores and corresponding change from baseline at each visit will be summarized descriptively by dose level group.

The motor domain of the Bayley III is a standard series of measurements to assess the motor (fine and gross motor subscales) development of infants and toddlers.

To calculate the raw scores the following steps will be required:

1. For each task performed the child can receive either a credit point (1) or no credit (0)
2. Establish the Basal aka “floor”:
 - 2a. Identify the age of the child in months to determine the “start point” item

Age	Start Point	Item Number
16 days – 1 month 15 days	A	1
1 month 16 days – 2 months 15 days	B	1
2 months 16 days – 3 months 15 days	C	5
3 months 16 days – 4 months 15 days	D	9
4 months 16 days – 5 months 15 days	E	9
5 months 16 days – 6 months 15 days	F	15
6 months 16 days – 8 months 30 days	G	19
9 months 0 days – 10 months 30 days	H	22
11 months 0 days – 13 months 15 days	I	35
13 months 16 days – 16 months 15 days	J	39
16 months 16 days – 19 months 15 days	K	42
19 months 16 days – 22 months 15 days	L	45
22 months 16 days – 25 months 15 days	M	48
25 months 16 days – 28 months 15 days	N	48
28 months 16 days – 32 months 30 days	O	51
33 months 0 days – 38 months 30 days	P	54
39 months 0 days – 42 months 15 days	Q	57

- 2b. If the child has three consecutive scores of 1 beginning with their ‘start point’ item, then this is the Basal aka “floor”.
- 2c. Otherwise, if any of the first 3 questions of the ‘start point’ are scored as 0, moving backwards towards 1, find the first instance prior to the initial start point where there are 3 consecutive questions with the score of 1. The first of these 3 will be the new “Basal”.
- 2d. If there are no instances of 3 consecutive scores of 1 occurring before the initial ‘start point’, then the “Basal” will be item 1 regardless of how the child scored on questions 1, 2 and 3.
3. Establish the “Ceiling”: the first time score of 0 appears on five consecutive items.
4. Count the number of items for which the child receives credit: “Basal” to “Ceiling”. Anything after the “ceiling” value is considered as score 0 regardless of what’s entered.
5. Count the number of items preceding the “Basal”. Usually these will be un-administered, but there are instances where these questions have been administered despite the later ‘start point’. Regardless of whether they are administered or un-administered, all the scores prior to the “Basal” should be counted as receiving credit (1).
6. Sum the numbers from step 4 and 5 to receive the raw score.

4.5.1.2.4 Change from baseline in total raw score in the fine motor domain of the Bayley-III at Week 24

The raw Bayley-III fine motor domain scores and corresponding change from baseline at each visit will be summarized descriptively by dose level group.

The motor domain of the Bayley III is a standard series of measurements to assess the motor (fine and gross motor subscales) development of infants and toddlers.

To calculate the raw scores the following steps will be required:

7. For each task performed the child can receive either a credit point (1) or no credit (0)
8. Establish the Basal aka “floor”:
 2a. Identify the age of the child in months to determine the “start point” item

Age	Start Point	Item Number
16 days – 1 month 15 days	A	1
1 month 16 days – 2 months 15 days	B	1
2 months 16 days – 3 months 15 days	C	1
3 months 16 days – 4 months 15 days	D	5
4 months 16 days – 5 months 15 days	E	10
5 months 16 days – 6 months 15 days	F	13
6 months 16 days – 8 months 30 days	G	15
9 months 0 days – 10 months 30 days	H	19
11 months 0 days – 13 months 15 days	I	22
13 months 16 days – 16 months 15 days	J	26
16 months 16 days – 19 months 15 days	K	28
19 months 16 days – 22 months 15 days	L	28
22 months 16 days – 25 months 15 days	M	31
25 months 16 days – 28 months 15 days	N	31
28 months 16 days – 32 months 30 days	O	35
33 months 0 days – 38 months 30 days	P	38
39 months 0 days – 42 months 15 days	Q	43

- 2b. If the child has three consecutive scores of 1 beginning with their ‘start point’ question, then this is the Basal aka “floor”.
 - 2c. Otherwise, if any of the first 3 questions of the ‘start point’ are scored as 0, moving backwards towards 1, find the first instance prior to the initial start point where there are 3 consecutive items with the score of 1. The first of these 3 will be the new “Basal”.
 - 2d. If there are no instances of 3 consecutive scores of 1 occurring before the initial ‘start point’, then the “Basal” will be item 1 regardless of how the child scored on questions 1, 2 and 3.
9. Establish the “Ceiling”: the first time score of 0 appears on five consecutive items.
 10. Count the number of items for which the child receives credit: “Basal” to “Ceiling”. Anything after the “ceiling” value is considered as score 0 regardless of what’s entered.
 11. Count the number of items preceding the “Basal”. Usually these will be un-administered, but there are instances where these questions have been administered despite the later ‘start point’. Regardless of whether they are administered or un-administered, all the scores prior to the “Basal” should be counted as receiving credit (1).
 12. Sum the numbers from step 4 and 5 to receive the raw score.

4.5.1.2.5 Change from baseline in the proportion of participants being able to feed without a gastrostomy or G-tube at Week 24

A participant’s ability to feed without a gastrostomy tube (G-tube) is evaluated by the Parental Swallowing Questionnaire. A participant score of “Never (0)” on the first item of the

questionnaire, “Since the last visit how often do you use the following with your child – Tube Feeding” will indicate that the participant met the criteria in the endpoint at the visit.

A shift table of the number and proportion of participants meeting the criteria described above will be presented by dose level. The shift from baseline G-tube status to best post-baseline G-tube status will be summarized, as well as the shifts to each visit.

4.5.1.2.6 Change from baseline in the Communicative Development Inventories scores at Week 24

The Communicative Development Inventories scores and corresponding change from baseline at each visit will be summarized descriptively by dose level group.

CDI scores for each participant will be calculated as number of items marked by caregiver/ number of items on questionnaire. This is a raw, unadjusted score.

4.5.1.2.7 Change from baseline in the Parental Global Impression of Secretion Severity (PGIS-S) score at Week 24

The PGIS-S scores and corresponding change from baseline at each visit will be summarized descriptively by dose level group.

Parents/LAR/caregiver will report on the amount of suctioning and secretions management required over the previous week, using a scale of 1 to 7 (1 = not affected and 7 = among the worst he has ever been) to report impression of change from baseline and impression of current severity.

Missing values will not be imputed.

4.5.1.2.8 Change in the Parental Global Impression of Secretion Improvement (PGIS-I) score at Week 24

The PGIS-I scores at each visit will be summarized descriptively by dose level group.

Parents/LAR/caregiver will report on the amount of suctioning and secretions management required over the previous week, using a scale of 1 to 7 (1=very much improved and 7 = very much worse) to report impression of change from baseline.

Missing values will not be imputed.

4.5.1.2.9 Change from baseline in Clinical Global Impression of Severity (CGI-S) at Week 24

The CGI-S scores and corresponding change from baseline at each visit will be summarized descriptively by dose level group.

A global assessment by the Investigator or designee will be done to assess the severity of the participant’s disease utilizing a 7-point scale, where 1 = Normal, shows no signs of illness and 7 = among the most extremely ill of participants.

Missing values will not be imputed.

4.5.1.2.10 Change in the Clinical Global Impression of Improvement (CGI-I) score at Week 24

The CGI-I scores at each visit will be summarized descriptively by dose level group.

A global assessment by the Investigator or designee will be done to assess if there has been any improvement of the participant's disease utilizing a 7-point scale, where 1 = very much improved and 7 = very much worse.

Missing values will not be imputed.

